2. **Any patient presenting grade 4 treatment-related AEs should have any relevant tests re-assessed at least within 72 hours until recovery to at least grade 3.**
3. Beta subunit-human chorionic gonadotropin (β -hCG) (urine or serum).
4. Cardiac rhythm will be identified in ECG intervals of at least 30 seconds of duration, PR interval, QT interval (raw), heart rate and QRS complex
5. A total of four blood samples (before PM01183 treatment start, 5 min before the end of PM01183 infusion, and 1 hour and 168 hours after the end of PM01183 infusion) will be collected for pharmacokinetic PM01183 analyses in Cycle 1 in patients treated in Arm A.
6. A total of four blood samples (before PM01183 treatment start, 5 min before the end of PM01183 infusion, and 1 hour and 168 hours after the end of PM01183 infusion) will be collected in a second cycle (between Cycle 2 and 4) in patients treated in Arm A. The second cycle with blood sample collection for PK will be assigned once the patient is randomized into the PM01183 arm.
7. One blood sample will be collected before treatment start in patients treated in Arm A (if informed written consent given) for the pharmacogenetic sub-study.
8. Patients who finish treatment without radiological PD will continue with the tumor assessments every eight weeks (\pm two weeks) from randomization until PD, start of a new antitumor therapy, death or date of study termination (clinical cutoff), whichever occurs first. After radiological PD is documented or a new antitumor therapy is started, patients will be followed for survival at least every three months (\pm two weeks) from the end-of-treatment visit until death or date of study termination, whichever occurs first. Once the whole recruitment is completed, the 3-month follow-up for patients who discontinue treatment due to PD will be performed according to a calendar time.
9. To be repeated only if baseline levels were higher than normal.
10. To be measured every eight weeks (at the same time than radiological tumor assessments) in case of discontinuation without disease progression or until start of a new antitumor therapy, death or date of study termination (clinical cutoff), whichever occurs first.
11. Patients withdrawn from the study with a drug-related AE should be followed every four weeks until recovery to at least grade 1 or stabilization.

Laboratory tests include:

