5.2 Sample Size

This phase III clinical trial is designed to determine a statistically significant difference in PFS by IRC between PM01183 and a control arm with PLD or topotecan in ovarian cancer patients with platinum-resistant disease.

Patients will be randomized to receive PM01183 given as 3.2 mg/m² (Arm A) or either topotecan or PLD (Arm B).

The prospective assumptions are a 30% reduction in the relative risk of progression or death (HR=0.7) to be achieved with the experimental arm (PM01183), at a one-sided 2.5% significance level with at least 90% power, following exponential distributions and fulfilling the proportional hazard assumption. Median PFS with control arm is expected to be around 3.5 months. It is forecasted that an observed HR of approximately 0.8 will have enough power to reject the null hypothesis (HR=1).

Approximately 420 patients with platinum resistant ovarian cancer will be necessary to stratify and randomize at a 1:1 ratio over 18 months (~23 patients/month). The required 332 PFS events are expected to occur around six months after randomization of the last patient. Therefore, the IDMC meeting after the IRC review to test PFS is expected to occur about one year after randomization of the last patient.

With the prospective assumptions above mentioned, about 175 PFS events are expected in the control arm and 157 in the PM01183 treatment arm.

The IDMC will review the results of the analyses. The IRC will determine the patient's best response and assign the date of objective response or progression/censoring according to the RECIST v.1.1.

5.2.1 *Futility Analysis*

A futility analysis will be performed when 210 patients are recruited (i.e., ~105 patients enrolled in each arm). The recruitment will not be put on hold.

In the futility analysis, the sponsor will make no claim of efficacy, consequently this futility analysis and the final analysis to reject the null hypothesis ($HR=1$) are planned; the significance level will be determined by the actual number of observed events by IR. To maintain scientific integrity, type II error will be controlled by a spending function defined by O'Brien-Fleming boundaries. Following the prospective assumptions, the interim analysis will occur at less than one year after start of recruitment. At this moment, with the available information collected after balancing efficacy and safety, the IDMC might recommend stopping the trial.

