Overall survival (OS) is defined as the time from the date of randomization to the date of death (death event) or last contact (in this case, survival will be censored on that date). If applicable and more than one OS analysis is performed type I error will be controlled by spending function defined by O'Brien-Fleming boundaries. Counting out subsequent therapies impact, sample size is powered to detect OS differences in the 20-30% range. Final OS analysis is planned 24 months after randomization of last patient (planned end of study date).

Landmark analyses of PFS at 6/12 months by IRC/IA and OS at 12/24 months will be the Kaplan-Meier estimates of the probability of being free from progression and/or alive at these time points.

Best antitumor response by IRC/IA will be the best response obtained in any evaluation according to RECIST v.1.1.

Radiological antitumor activity will be assessed using the RECIST v. 1.1 on a set of measurable lesions identified at baseline as target lesions, and/or non-measurable lesions (if any) identified at baseline as non-target lesions and followed until disease progression (PD) by the appropriate method [computed tomography (CT) scan or magnetic resonance imaging (MRI)].

Duration of response (DR) will be calculated from the date of first documentation of response (complete or partial response, whichever comes first) to the date of documented PD or death. The censoring rules defined above for PFS will be used for duration of response.

Assessments must be done consistently in both treatment arms to ensure a symmetrical assessment of tumor response and progression. Every effort should be made to ensure

that these assessments are done on the required date. Time to n^{th} (i.e. 1, 2, 3...) disease assessment is defined as weeks between randomization and the recorded date of the n^{th} radiology assessment after randomization.

Best response according to tumor marker evaluation (CA-125) will be the best response obtained according to GCIG criteria⁽¹⁾. Irrespectively of treatment arm, tumor marker assessment will be performed symmetrically at baseline and every eight weeks from randomization until evidence of PD.

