6.2 Efficacy Analysis Methods

Time-to-event variables (PFS, OS and DR) and their set time estimates (i.e., PFS 6/12 and OS 12/24) will be analyzed according to the Kaplan-Meier method.

The stratified log-rank test, using actual values for all randomization strata variables, on the ITT population will be primarily used to compare the time-to-event variables. If the actual value is not a pre-defined category the value will be added to the most similar category (e.g., patients with more than three prior chemotherapy lines will be included in the 3-lines category).

Unstratified log-rank tests will also be calculated as supportive analyses.

The symmetry of tumor evaluations between the different arms will be examined. Wilcoxon test to compare time to disease assessments between treatment arms will be used to assess symmetry of evaluations. Moreover, Kaplan-Meier curves of the time from randomization and first and second disease assessment will be plotted. If necessary, internal symmetry between the two different treatments in the control arm will be checked following the same approach.

Cox regression will be used to calculate the risk reduction (PFS, OS and DR) and to evaluate the influence of the stratification variables and other potential prognostic factors on the time-to-event efficacy endpoints.

Counts and percentages, with their corresponding exact 95% confidence intervals, will be calculated for the binomial endpoints (i.e., response rate). The Fisher's exact test (univariate analyses) and logistic regressions will be used to compare the response rates.

Waterfall plots will be used to describe the best variation of the sum of target lesions diameters during the treatment.

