11.3 Efficacy Analysis

Efficacy analysis will be carried out on the ITT population.

Table 11.3.1.1 PFS by IRC (primary analysis)

Variable	Stratification factors	p-value*
Treatment arm (main analysis)	Actual values	
Treatment arm (sensitivity)	Values reported for randomization	

*Stratified log rank test.

Progression-free survival by IRC

Table 11.3.1.2 Median FU for PFS by IRC

		Total (PM01183 and Control)
Follow-up (descriptive way)		Median (range)
Follow-up (reverse censoring method)		Median (95%CI)

Table 11.3.1.3 PFS by IRC

	PM01183	Control	Parameter	p-value
N				
Events				
Censored				
Median PFS (95% CI)			Log-Rank: HR (95% CI) :	LR: HR:
PFS at 6 months (95% CI)			Diff:	
PFS at 12 months (95% CI)			Diff:	

Kaplan Meier plot (Figure 11.3.1.3) will be shown too.

Table 11.3.1.4 Multivariate analysis of PFS by IRC (Stratification factors and treatment arm)

Analysis of maximum likelihood estimates								
Variable label	Variable values	DF	Parameter estimate	Standard error	Chi-square	Pr > ChiSq	Hazard ratio	95% Hazard ratio confidence limits

Table 11.3.1.5 Multivariate analysis of PFS by IRC

Analysis of maximum likelihood estimates								
Variable label	Variable values	DF	Parameter estimate	Standard error	Chi-square	Pr > ChiSq	Hazard ratio	95% Hazard ratio confidence limits

(see list of covariates in section 6.2).

Table 11.3.1.6 Proportional hazard assumption and restricted mean survival for PFS by IRC

Variable	PM01183	Control	Interaction p-value
Restricted mean survival [*]			

*It will be calculated if proportional hazard assumption is not met.

A forest plot (Figure 11.3.1.7) summarizing main results, stratification factors and covariates in terms of PFS by IRC will be plotted.

Progression-free survival by IA

Table 11.3.1.8 PFS by IA (Stratified log rank test)

Variable	Stratification factors	p-value*
Treatment arm (main analysis)	Actual values	
Treatment arm (sensitivity)	Values reported for randomization	

*Stratified log rank test.

Table 11.3.1.9 Median FU for PFS by IA

	Total (PM01183 and Control)
Follow-up (descriptive way)	Median (range)
Follow-up (reverse censoring method)	Median (95%CI)

Table 11.3.1.10 PFS by IA

	PM01183	Control	Parameter	p-value
N				
Events				
Censored				
Median PFS (95% CI)			Log-Rank: HR (95% CI) :	LR: HR:
PFS at 6 months (95% CI)			Diff:	
PFS at 12 months (95% CI)			Diff:	

Kaplan Meier plot (Figure 11.3.1.10) will be shown too.

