PR					
SD					
PD					
Unknown*					
CR+PR; n (%) and binomial exact 95% confidence interval					

(*) Including NE, non-responders and insufficient data available.

Table 11.3.1.30 Multivariate analysis of response rate by IRC (Stratification factors and treatment arm)

Table 11.3.1.31 Multivariate analysis of response rate by IRC

(See list of covariates in section 6.2).

A forest plot (Figure 11.3.1.32) summarizing main results, stratification factors and covariates in terms of response by IRC will be plotted.

A waterfall plot (Figure 11.3.1.33) describing the best variation of the sum of target lesions during the treatment will be plotted.

Table 11.3.1.34 DR by IRC

	PM01183	Control	Parameter	p-value
N				
Events				
Censored				
Median DR (95% CI)			Log-Rank: HR (95% CI) :	LR: HR:

Objective response and duration of response by IA

Table 11.3.1.35 Response rate by IA

Response	PM01183		Control		p-value
	N	%	N	%	
CR					
PR					
SD					
PD					
Unknown*					
CR+PR; n (%) and binomial exact 95% confidence interval					

(*) Including NE, non-responders and insufficient data available.

Table 11.3.1.36 Multivariate analysis of response rate by IA (Stratification factors and treatment arm)

Table 11.3.1.37 Multivariate analysis of response rate by IA

Analysis of maximum likelihood estimates								
Variable label	Variable values	DF	Estimate	Standard error	Wald chi-square	Pr > ChiSq	Odds ratio estimate	95% Wald confidence limits

(See list of covariates in section 6.2).

A forest plot (Figure 11.3.1.38) summarizing main results, stratification factors and covariates in terms of response by IA will be plotted.

A waterfall plot (Figure 11.3.1.39) describing the best variation of the sum of target lesions during the treatment will be plotted.

Table 11.3.1.40 DR by IA

	PM01183	Control	Parameter	p-value
N				
Events				
Censored				
Median DR (95% CI)			Log-Rank: HR (95% CI) :	LR: HR:

CA-125 Objective response

Table 11.3.1.41 CA-125 response rate

Response	PM01183		Control		p-value
	N	%	N	%	
CR					
PR					
SD					
PD					
Unknown*					
CR+PR; n (%) and binomial exact 95% confidence interval					

(*) Including NE, non-responders and insufficient data available.

Table 11.3.1.42 CA-125 response rate (excluding UK category)

Response	PM01183		Control		p-value
	N	%	N	%	
CR					
PR					
SD					
PD					
CR+PR; n (%) and binomial exact 95% confidence interval					

Progression and censoring reasons by IRC/IA

Table 11.3.1.43 Progression type by IRC/IA

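### The CA-125 table that drops the Unknown category would, as its footnote is worded, also drop any non-responders coded Unknown and so could overstate the response rate

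*SAP*

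**What the plan says.** CA-125 best response is a listed secondary endpoint (SAP 4.3). SAP 6.1 defines it only by reference to external criteria: it "will be the best response obtained according to GCIG criteria". Section 11.3 sets the population: "Efficacy analysis will be carried out on the ITT population".

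Two table shells in section 11.3 report the endpoint.

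- Table 11.3.1.41 has rows for CR, PR, SD, PD and Unknown. The footnote to Unknown reads "Including NE, non-responders and insufficient data available".
- The second is headed "Table 11.3.1.42 CA-125 response rate (excluding UK category". It has rows for CR, PR, SD and PD, no Unknown row and no footnote of its own. The SAP's abbreviation list gives UK as Unknown.

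Both shells end with the row "CR+PR; n (%) and binomial exact 95% confidence interval" and have a p-value column. SAP 6.2 prescribes exact intervals and Fisher's exact test for response rates.

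A note to the Protocol's schedule of assessments restricts CA-125 after baseline: "To be repeated only if baseline levels were higher than normal". Neither document defines a CA-125-evaluable population or says what a non-responder is for this endpoint.

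**The concern.** A table limited to assessable patients should remove people because their response could not be determined. Here the removed category is defined to contain some people because they did not respond. For that subset, exclusion depends on the outcome being measured: the numerator keeps all responders and the denominator loses some failures.

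Two things are at stake. The CR+PR rate and its interval in Table 11.3.1.42 could be too high in either arm. The between-arm p-value could also be distorted, in either direction, if the arms differ in how many non-responders are coded Unknown. Randomization does not protect a comparison whose denominator is chosen partly by outcome.

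**Working it through.** The plan states no CA-125 response rate and no expected Unknown share, so there is no figure to reproduce. The check is on the denominators.

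**Notation, per arm**
- N: patients randomized. About 210 per arm, from the planned 420 at 1:1 (SAP 5.2).
- x: patients with CR or PR.
- a: patients coded Unknown because they are NE or have insufficient data.
- b: patients coded Unknown as non-responders.

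**Rates**
- Table 11.3.1.41 (full denominator): x/N.
- Table 11.3.1.42 as worded: x/(N−a−b).
- Evaluable rate, removing only the unassessable: x/(N−a).

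The rise from the first table to the second splits into two factors:

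N/(N−a−b) = [N/(N−a)] × [(N−a)/(N−a−b)]

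The first factor is the legitimate effect of restricting to assessable patients. The second is the error. It exceeds 1 whenever b > 0 and equals 1 when b = 0.

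**Illustration, one arm.** Assumed: N = 210, x = 42, and 63 patients (30%) coded Unknown. Table 11.3.1.42 then shows 42/147 = 28.6% whatever the split of the 63.

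| Share of Unknown who are non-responders | b | a | Evaluable rate x/(N−a) | Error factor (N−a)/147 |
|---|---|---|---|---|
| 0% | 0 | 63 | 42/147 = 28.6% | 1.00 |
| 25% | 16 | 47 | 42/163 = 25.8% | 1.11 |
| 50% | 32 | 31 | 42/179 = 23.5% | 1.22 |
| 75% | 47 | 16 | 42/194 = 21.6% | 1.32 |
| 100% | 63 | 0 | 42/210 = 20.0% | 1.43 |

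In the 50% row the legitimate factor is 210/179 = 1.17 and the error factor is 179/147 = 1.22. Their product is 210/147 = 1.43.

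**Interval.** Assumed: 63 responders of 210 and 63 coded Unknown, all non-responders (a = 0). The correct rate is 30.0% (exact 95% CI 23.9% to 36.7%). The table would show 63/147 = 42.9% (34.7% to 51.3%).

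**Comparison between arms.** Assumed: 210 per arm and a = 0.
- 42 responders in each arm, so no true difference. With 20% of each arm coded Unknown, the table shows 42/168 = 25.0% in both, p = 1.0. With 40% (84) against 10% (21), it shows 42/126 = 33.3% against 42/189 = 22.2%, Fisher p = 0.037.
- 63 against 42 responders, a true difference of 30.0% − 20.0% = 10.0 points. With 10% (21) against 30% (63) coded Unknown, the table shows 63/189 = 33.3% against 42/147 = 28.6%, a difference of 4.8 points.

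These cases show direction only. The 40% against 10% split is chosen to show what is possible and is not a forecast.

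**The case against.** The strongest reply is that the footnote is template wording with little effect. The same footnote sits under the RECIST response tables, 11.3.1.29 and 11.3.1.35. All these tables already have SD and PD rows, so the term presumably does not mean patients classed SD or PD. It may mean patients counted as failures because no category could be assigned, which is close to NE. On that reading no assessable patient is lost and the inflation is zero. Whether a CA-125 non-responder can fall outside SD and PD depends on the GCIG criteria, which the SAP cites but does not reproduce.

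It can also be said that an assessable-only table is reasonable, because patients without a raised baseline have no planned repeat values. Table 11.3.1.41 is reported as well and shows how many patients were coded Unknown.

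Much of this stands. The meaning of the term is not settled, the table has a proper purpose, and the full-denominator table limits the harm. But if no assessable non-responder is meant to be in Unknown, the word does not belong in the footnote. The RECIST tables have no version excluding Unknown, so the wording is harmless there; for CA-125 it fixes a denominator. SAP 8.8, which leaves missing values out of calculations, could cover NE and insufficient data, but a known non-response is not a missing value. Table 11.3.1.42 also has its own interval and p-value and could be cited alone.

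A reader might infer that the table removes all CA-125 non-responders, or that the reported rate is bound to be inflated. The documents support neither. Patients classed SD or PD remain in the denominator, and nothing says how many non-responders, if any, will be coded Unknown.

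**Conclusion.** Wrong as written; minor. On the plain wording, Table 11.3.1.42 excludes any non-responder coded Unknown and keeps every responder, so its CR+PR rate, interval and p-value could be biased. The rate is overstated by the factor (N−a)/(N−a−b). The direction for each arm's rate is certain if b > 0; the between-arm comparison can move either way.

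The size cannot be derived from the documents. The illustrative factors of 1.00 to 1.43 rest on an assumed 30% coded Unknown and an assumed split of that group. Only the part due to b is an error; removing patients who cannot be assessed is legitimate. Table 11.3.1.41, the RECIST response rates, OS and the primary PFS analysis are not affected. CA-125 response is also absent from the main summary of efficacy analyses in SAP 6.2.

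**What to change.** Make two edits to SAP 11.3.

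1. In the Unknown footnote to Table 11.3.1.41, delete the reference to non-responders, leaving NE and insufficient data. Assessable patients without a response are then counted under SD or PD, or otherwise kept in the denominator. A separate non-responder row is not advised, because it could overlap with SD and PD.
2. Under Table 11.3.1.42, state that it excludes only patients not evaluable for CA-125 response: NE or insufficient data, including those whose baseline was not raised and who therefore have no repeat values. Give the resulting denominator for each arm.

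The cost is one footnote edit and one denominator statement, made before the data are analyzed. No new data are needed, and the assessable-only table is kept.
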